Table 1: Blood Testing Schematics.....	13
Table 2: Summary of data within specified mg/dL of the comparator method for glucose concentrations across the entire range.....	24
Table 3. Summary of data within specified mmol/L of the comparator method for β-ketone concentrations across the entire range.....	24

	Method Comparison/User Evaluation of the i-SENS Self-Monitoring Blood Glucose / β-Ketone System(CareSens PRO GK BT)	Document No. BGM-2205084
	Authorized approval of controlled documents is required for external release.  Controlled Document /  Uncontrolled Document	Version No. 2

ABBREVIATIONS

AE	Adverse Event
BG	Blood Glucose
CRF	Case Report Form
DD	Device Deficiency
GCP	Good Clinical Practice
HCP	Health Care Professional
ICF	Informed Consent Form
ID/GC/MS	Isotope Dilution Gas Chromatography Mass spectrometry
IRB	Institutional Review Board
JCTLM	Joint Committee for Traceability in Laboratory Medicine
NCCLS	National Committee for Clinical Laboratory Standards
PI	Principal Investigator
RX Imola	Randox Imola D-3-Hydroxybutyrate (Ketone) analyzer (Randox Laboratories)
SAE	Serious Adverse Event
SMBG	Self-Monitoring of Blood Glucose
UADE	Unanticipated Adverse Device Effect
YSI	YSI 2300 Stat Plus Glucose Analyzer (YSI Incorporated)

	Method Comparison/User Evaluation of the i-SENS Self-Monitoring Blood Glucose / β-Ketone System(CareSens PRO GK BT)	Document No. BGM-2205084
	Authorized approval of controlled documents is required for external release.  Controlled Document /  Uncontrolled Document	Version No. 2

1. Background Information

The CareSens PRO GK BT Blood Glucose/Blood β -Ketone Monitoring System is used for the quantitative measurement of the glucose/ β -ketone level in capillary whole blood as an aid in monitoring diabetes management effectively at home. The CareSens PRO GK BT Blood Glucose/Blood β -Ketone Monitoring System includes the Meter, Blood Glucose Test Strips/Blood β -Ketone Test Strips, a user's manual, a quick reference guide, batteries, lancets, a lancing device and a carrying case. Two levels of control solutions (control level A and B) for glucose test and two levels of control solutions (control level A and B) for β -ketone test are also associated with the test system.

This in vitro diagnostic system requires 0.4 μ L of blood and delivers results in 5 seconds for the glucose test and 0.5 μ L of blood and delivers results in 8 seconds for the β -ketone test. It contains a meter memory of up to 1000 test results with time and date. The system has an optional strip expiration date indicator, hypoglycemia / hyperglycemia indicator and adjustable alarm features.

The CareSens PRO GK BT meter can calculate and display the averages of total test results, pre-meal test results, post-meal test results and fasting test results, from the past 1, 7, 14, 30 and 90 days if the appropriate information has been provided to the meter. The meter is designed to minimize code related errors in monitoring by using a no-coding function.

The clinical trial will assess the accuracy and usability of the meter in untrained subjects with or without diabetes or pre-diabetes.

The clinical trial will follow the requirements described in the FDA Guidance for Self-Monitoring Blood Glucose (SMBG) Test Systems for Over-the-Counter Use (Section VI. PERFORMANCE EVALUATION FOR SMBGs, Section C) for glucose, and CLSI EP09-A3 Measurement Procedure Comparison and Bias Estimation Using Patient Samples for β -ketone.

2. Study Objectives and Purpose

The method comparison and user evaluation study are designed for the assessment of both system accuracy in the hands of the intended users as well as other aspects to support lay use, such as a labeling assessment and usability.

Objectives

- To determine if untrained people with or without diabetes or pre-diabetes can obtain acceptable glucose and β -ketone results from fingerstick capillary blood.
- Glucose: 95% of all glucose results in the study should be within $\pm 15\%$ of the comparator results across the entire claimed measuring range of the device and 99% of all SMBG results within $\pm 20\%$ of the comparator results across the entire claimed measuring range of the device.
- β -ketone: 95% of the individual ketone results in this study should be within $\pm 0.3\text{mmol/L}$ at concentration $< 1.5\text{mmol/L}$ and within $\pm 20\%$ at concentration $\geq 1.5\text{mmol/L}$ of the comparator results.

3. Study Design

A draft device labeling (which have undergone a Flesch and Kincaid reading assessment), is given to the study subjects and no other training or assistance from a trained study staff/technician is provided to the user.

	Method Comparison/User Evaluation of the i-SENS Self-Monitoring Blood Glucose / β-Ketone System(CareSens PRO GK BT)	Document No. BGM-2205084
	Authorized approval of controlled documents is required for external release.  Controlled Document  Uncontrolled Document	Version No. 2

A minimum of 10 test strip vials/packages covering a minimum of 3 test strip lots are included in the test. The test strips will have undergone typical shipping and handling conditions from the site of manufacture to a U.S. site prior to being used in the study.

Taking into consideration of a “worst-case scenario”, the strips used in the method comparison/user evaluation shall have undergone a container shipping by sea (approximately 60 days) and its shipping and handling records shall be kept.

Study testing procedures are conducted by trained study staff/technicians familiar with all aspects of the protocol, documentation, forms, use of the investigations and commercially available SMBG, data collection and GCP. All training will be documented and filed.

Glucose

Following the FDA SMBG Guidance, at least 350 evaluable and different subjects, which meet the inclusion/exclusion criteria, are to be included in the user evaluation of the Self-Monitoring Blood Glucose Test Systems (i.e. SMBG). These results will be compared to results from the reference equipment (YSI STAT Plus 2300 glucose analyzer). From the minimum of 350 evaluable subjects, at least 10 fingerstick capillary blood samples shall be < 80 mg/dL and >250 mg/dL respectively. Therefore the number of subjects may exceed 350 until the specified glucose concentration ranges are filled.

β -ketone

The test results are to be analyzed based on the CLSI EP09-A3 guideline through method comparison analysis using capillary blood samples. The performance is evaluated with a minimum of 350 capillary blood samples and compared to results from the reference equipment (Randox Imola D-3-Hydroxybutyrate analyzer). From the minimum of 350 evaluable subjects, at least 10 fingerstick capillary blood samples shall be ≥ 1.5 mmol/L.

4. Selection and Withdrawal of Subjects

4.1 Subject Recruitment

Recruiting will be done by the PI and trained study staff at the clinical site.

4.2 Informed Consent

Consent will be obtained before the study commences at the clinical site by the PI and trained study staff. In obtaining and documenting informed consent, the investigator must comply with applicable regulatory requirement(s) and adhere to ICH GCP and the requirements in the Declaration of Helsinki before any study-related activity.

The investigator or designee must give the subject verbal and written information about the study and the procedures involved in a form that the subject can read and understand. The subjects must be fully informed of their rights and responsibilities while participating in the study as well as possible disadvantages.

The investigator or designee must ensure the subject has ample time to come to a decision whether or not to participate in the study. Study subjects will be given the opportunity to ask questions. A voluntary, signed and personally dated informed consent must be obtained from the subject before any study-related activity.

	Method Comparison/User Evaluation of the i-SENS Self-Monitoring Blood Glucose / β-Ketone System(CareSens PRO GK BT)	Document No. BGM-2205084
	Authorized approval of controlled documents is required for external release.  Controlled Document  Uncontrolled Document	Version No. 2

The responsibility for seeking informed consent must remain with the investigator, but the investigator may delegate the task to a properly trained person, in accordance with local requirements. The written informed consent must be signed and personally dated by the person who obtained the informed consent before any study-related activity.

If information becomes available that may be relevant to the subject's willingness to continue participating in the study, the investigator must inform the subject in a timely manner, and a revised written subject information must be provided, and a new informed consent must be obtained. The informed consent describes the study, what is expected of the subject during the study, its potential risks, the subject's privacy rights under HIPAA (Health Insurance Portability and Accountability Act of 1996), and the details of participation.

4.3 Inclusion/Exclusion Criteria

The subjects enrolled are assigned a screening number and will be assessed for study subject inclusion/exclusion criteria.

Inclusion Criteria:

- Males and females, 18 years of age and older
- People with type 1 diabetes, type 2 diabetes, pre-diabetes and no diabetes (self- reported)
- Able to speak, read and understand English (subjects must demonstrate ability to read a sentence from a page of the draft device labeling instructions (user's manual) to qualify for the study)
- Willing to complete all study procedures
- Has read, understood, and signed the Informed Consent Form

Note: The study group consists of naive SMBG users and non-naive SMBG users. At least 10% of study participants should be naive for SMBG, including subjects without diabetes.

Exclusion Criteria:

- Hemophilia or any other bleeding disorder
- Works for a medical laboratory, hospital, other clinical setting or a medical device company that involves training on or clinical use of blood glucose meters
- Physical, visual or neurological impairments as determined by the investigator or designee that would make the subject unable to perform self-testing (reason for exclusion will be clearly documented by investigator or designee directly on the subject disposition form)
- A condition, which in the opinion of the investigator or designee, would put the subject or study conduct at risk (reason for exclusion will be clearly documented by investigator or designee on the subject disposition form).

Note 1: In the event of a physical, visual or neurological impairment that makes it difficult for a subject to complete the questionnaire, the subject's verbal responses will be accepted and should be appropriately documented as such within the subject records form.

	Method Comparison/User Evaluation of the i-SENS Self-Monitoring Blood Glucose / β-Ketone System(CareSens PRO GK BT)	Document No. BGM-2205084
	Authorized approval of controlled documents is required for external release.  Controlled Document /  Uncontrolled Document	Version No. 2

Note 2: Evaluable data from all eligible subjects in the study will be included even if more than 350 samples are collected; no eligible subject data will be excluded from the data analysis. (See section 5.8.3. Data Evaluability).

Upon meeting the inclusion/exclusion criteria, a unique subject number is assigned. The trained study staff will collect self-reported subject demographics, diabetes (or pre-diabetes) history, self-monitoring of blood glucose/ β -ketone history, education background and other information relevant to the study and to the ability to use a meter.

4.4 Study Termination and Subject Withdrawal Criteria

Subjects may be withdrawn from the study at their own request for any reason or at the discretion of the PI (or designee) for one of the following reasons:

- Adverse Event [See section 7]
- Illness of a subject
- Subject non-compliance with protocol requirements
- Other, at the discretion of the investigator

In such cases, the subject will be withdrawn from further study participation. Data collected from withdrawn subjects will be analyzed and results will be retained for safety assessments. If available, data will be retained in analyses related to the objectives of the study unless there is a valid reason to believe that the data may be biased, incorrect, or confounded.

5. Materials and Methods

5.1 Materials and Equipment

- CareSens PRO GK BT meters
- Test strips (glucose/ β -ketone): at least 3 lots, at least 10 vials/packages
- CareSens PRO GK BT user's manual, and quick reference guide
- Control solutions: CareSens PRO (glucose) level A and level B and KetoSens (β -ketone) level A and B
- Spare batteries for meters
- A commercially approved SMBG meter, control solution(s), and user's manuals
- YSI 2300 STAT Plus glucose analyzer (YSI) YSI reagent and YSI supplies
- Randox Imola D-3-Hydroxybutyrate (Ketone) analyzer (Rx Imola)
- Randox reagent and Randox supplies
- Thermo-hygrometer
- Micro centrifuge

	Method Comparison/User Evaluation of the i-SENS Self-Monitoring Blood Glucose / β-Ketone System(CareSens PRO GK BT)	Document No. BGM-2205084
	Authorized approval of controlled documents is required for external release.  Controlled Document  Uncontrolled Document	Version No. 2

- Tenderlett™ or tenderlett-like single use lancing device (single device for each subject)
- Lancing devices and lancets (single device for each subject)
- Heparinized collection tubes
- Micro hematocrit tubes, sealant, micro hematocrit tube reader
- Syringes and needles
- Pipettes
- Alcohol wipes
- Gauze
- Band-Aids
- Eppendorf tubes
- Kim wipes
- Clorox Germicidal wipes (EPA#: 67619-12)
- Non-latex gloves
- Supplies to treat hypoglycemia
- Laboratory coats
- Safety goggles
- Biohazard Sharps container

5.2 Preparation and Administration

Study materials will be provided by the sponsor and shipped, or hand carried to the clinical site by the sponsor (or sponsor representative).

The applicable serial and lot numbers for materials and equipment should be recorded upon receipt.

Storage

The investigational device must be stored in an area that is secure and accessible to trained study staff only.

Dispensing of Study Investigational Device and Materials

Dispensation of the investigational device and study materials will be performed by the individuals responsible for conducting the study at the clinical site per the Delegation of Authority Log.

Return of Study Investigational Device and Materials

All study related materials will be collected by the sponsor (or sponsor representative) upon completion of the study.

	Method Comparison/User Evaluation of the i-SENS Self-Monitoring Blood Glucose / β-Ketone System(CareSens PRO GK BT)	Document No. BGM-2205084
	Authorized approval of controlled documents is required for external release.  Controlled Document  Uncontrolled Document	Version No. 2

Device Accountability

It shall be the sponsor's responsibility to ensure that an accurate record of investigational devices issued and returned is maintained.

All investigational devices will be retrieved at the conclusion of the study. The devices are assumed to be contaminated and will require to be handled as such (Standard precautions).

The devices will undergo disinfection per validated disinfection procedure prior to further analysis.

5.3 Preparatory Steps by the Trained Study Staff

Prior to first use, the meters will have times and dates preset to the time zone of use.

5.3.1 Labeling

The meters and strip lot vials/packages shall bear a label in accordance with Title 21 CFR 812.5 with the following information:

“CAUTION-Investigational device. Limited by United States law to investigational use.”

5.3.2 Safety and Disinfection procedures

- 1) Only the trained study staff will perform disinfection procedures.
- 2) The meters will be used by multiple subjects in this study; therefore the meters must be disinfected between subjects.
 - (1) Open the cap of the Clorox Germicidal Wipes container and pull out 1 towelette and close the cap.
 - (2) Wipe the entire surface of the meter 3 times horizontally and 3 times vertically using one towelette to pre-clean blood and other body fluids.
 - (3) Dispose of the used towelette in a trash bin.
 - (4) Pull out 1 new towelette and wipe the entire surface of the meter 3 times horizontally and 3 times vertically using a new towelette to remove blood borne pathogens.
 - (5) Dispose of the used towelette in a trash bin.
 - (6) Allow exteriors to remain wet for 1 minute, and then wipe the meter using a Kim wipe.
- 3) The meters must also be disinfected after use by the trained study staff prior to shipment back to i-SENS and at any time a meter becomes contaminated with blood.
- 4) A new lancing device will be provided to each subject. At the end of the subject's visit, the lancing device will be discarded or given to the subject to keep.
- 5) The lancets used in the study are single-use and will be disposed of in a biohazard sharps container after use.
- 6) Trained study staff will wear disposable non-latex exam gloves during study procedures where the risk of transmission of disease is present. These procedures include performing blood glucose and β -ketone measurements, sample processing, and laboratory procedures involving blood and plasma

	Method Comparison/User Evaluation of the i-SENS Self-Monitoring Blood Glucose / β-Ketone System(CareSens PRO GK BT)	Document No. BGM-2205084
	Authorized approval of controlled documents is required for external release.  Controlled Document  Uncontrolled Document	Version No. 2

samples. Trained study staff in contact with the subjects will use a new pair of gloves for each subject and will change gloves between subjects.

- 7) Trained study staff will record all the meter results on the appropriate form. If the meter has turned off and results are difficult to see, the meter memory will be reviewed, and the results will be obtained from the meter memory.
- 8) Disposable bench top covers to cover the work areas where body fluids and risk of disease transmission are present must be changed between subjects. Hard surfaces will be disinfected between subjects.
- 9) A commercially approved device may be used for determining the subject's glucose/ β -ketone level during the study as needed for safety reasons or to ascertain the glucose/ β -ketone level for study reasons. The meter will be disinfected between subjects following the manufacturer's disinfecting instructions.
- 10) All the CareSens PRO GK BT meters used in the study will be tested using control solutions, Level A and B of CareSens Pro control solution for the glucose and level A and level B of KetoSens control solution for the β -ketone and recorded at the beginning and at the end of each clinical study day and at any time it is suspected that the meter and test strips are not working properly. If the results are out of range, troubleshooting will be performed (see the user's manual) and the control test will be repeated (a total of three (3) attempts per control test are allowed). If the meter tests are out of range after troubleshooting is complete, the meter will be removed from the study. The meters that failed control solution testing and were removed from the study will be recorded and reported. This will be documented on the Device Deficiency Form.

5.3.3 Temperature and Humidity Monitoring

The trained study staff will measure the temperature and humidity in the testing area(s) three times per day: prior to first subject of the day, halfway through the day, and after all subjects completed that day. This will be done using a thermometer/hygrometer supplied by the clinical site and the results will be recorded on the appropriate form.

5.4 Subject Evaluation Procedure

Each subject is provided with all the materials needed for blood glucose/ β -ketone self-testing.

- 1) The subjects are given sufficient time to review the user's manual and the quick reference guide. No training is provided by the trained study staff.

Note: The subjects should obtain their own fingertip capillary sample and perform a test using only the draft device labeling as instructions (user's manual and the quick reference guide). No other training or prompting should be provided to the subject and no assistance should be given from the trained study staff. The subjects should be sequestered in different stations that they cannot observe or be influenced by the testing technique of other subjects or trained study staff.

- 2) The subject washes his/her hands with warm water and soap, rinses and dries well.
- 3) The subject lances his/her finger using a lancing device and performs a blood glucose test with a glucose test strip on the meter. Three successful fingersticks/lances are allowed maximum (actual lances on the finger) to get a meter result. The lancet should be changed after each actual fingerstick. The trained study staff records the times of the meter tests, results, number of successful lances, and marks whether the subject completed all steps on the CRF.

	Method Comparison/User Evaluation of the i-SENS Self-Monitoring Blood Glucose / β-Ketone System(CareSens PRO GK BT)	Document No. BGM-2205084
	Authorized approval of controlled documents is required for external release.  Controlled Document  Uncontrolled Document	Version No. 2

4) Immediately within 5 minutes of the first evaluable meter reading, the trained study staff collects more blood for YSI and hematocrit measurement (approx. 300-350 μ L) using a Tenderlett TM or tenderlett-like single use lancing device. A total of up to 3 additional lancings are allowed to collect blood in the collection tubes. Centrifuge blood within 10 minutes of sample collection and conduct YSI within 20 minutes of centrifugation. Maximum of 35 minutes to complete from evaluable meter result. After measuring blood glucose, the subject lances his/her finger and performs a β -ketone test with a β -ketone test strip on the same meter. The trained study staff /technician records the times of the meter tests, results, number of successful lances, and marks whether the subject completed all steps on the CRF.

Note: The meter automatically recognizes the measuring strip when each strip is inserted. If the KetoSens strip is inserted, KETONE will appear on the result window.

5) Immediately within 5 minutes of the first evaluable meter reading, the trained study staff collects more blood for Rx Imola measurement (approx. 500~550 μ L) using a Tenderlett TM or tenderlett-like single use lancing device. A total of up to 3 additional lancings are allowed to collect blood in the collection tubes. Centrifuge blood within 10 minutes from sample collection and conduct Rx Imola measurements within 20 minutes of centrifugation. Maximum of 35 minutes to complete from evaluable meter result.

6) Collect more blood and fill two micro hematocrit tubes for hematocrit test. The blood for hematocrit test can be taken from one of fingersticks already done.

Note: The subject's hematocrit measurement should be within 20-60% in order for the result to be considered evaluable.

7) For any occurrence of meter errors, the subject should follow the instructions in the user's manual.

8) The time of each test, meter results, any occurrence of meter error codes is recorded by the trained study staff on CRF.

9) Each evaluable fingerstick meter results are compared to the capillary YSI results and Rx Imola results. (More than one comparator measurement results averaged for each sample)

NOTE: If plasma cannot be measured immediately using YSI and Rx Imola within 15 mins after blood collection (in case of analyzer correction or device malfunction), store the plasma separated from the blood collection tube refrigerated.

For the study, multiple meters will be used and strips of at least 10 vials/packages over at least 3 lots will be used and rotated.

Table 1. Blood Testing Schematic

Fingerstick testing	

 • Select strips for subject blood testing (Lot A, Lot B and Lot C rotated) • Record time of 1st test 	
Glucose First lancing	
	Subject test
	
 • Study Staff records time of test, result of glucose and if subject completed each step properly (check boxes on CRF), and if subject encountered any problems.
Tenderlett or similar (Study Staff) stick	
	For YSI testing

 • Immediately following meter test (\leq5 minutes), study staff lances subject fingertip • Record time of lancing • Collect blood in Sodium Heparin tube (approx. 300-350 μL) 	

	Method Comparison/User Evaluation of the i-SENS Self-Monitoring Blood Glucose / β-Ketone System(CareSens PRO GK BT)	Document No. BGM-2205084
	Authorized approval of controlled documents is required for external release.  Controlled Document  Uncontrolled Document	Version No. 2

 • Centrifuge blood and record time (should be within 10 minutes of sample collection) • Test the sample and record time and result of glucose on CRF 	
β-ketone Second lancing	Subject test

 • Study Staff records time of test, result of β-ketone and if subject completed each step properly, and if subject encountered any problems. 	
Tenderlett or similar (Study Staff) stick	For Rx Imola testing

 • Immediately following meter test (\leq5 minutes), study staff lances subject fingertip • Record time of lancing • Collect blood in Sodium Heparin tube (approx. 500 ~ 550μL) • Centrifuge blood and record time (should be within 10 minutes of sample collection) • Test the sample and record time and result of glucose on CRF 	
Hematocrit Testing	

 • Fill 2 micro hematocrit tubes and record time and result of hematocrit 	
Record meter reading or meter error codes or subject errors as appropriate	

Note: Trained study staff should use a new pair of gloves for each subject and should change gloves between subjects.

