8.6 Investigator's Report of Study Closure

The Study Monitor will send a letter to the site informing them that the study is closed. The study will be considered closed when all the required data has been acquired for data analysis.

The Investigator or designee will submit a report summarizing subject disposition and other study details, as appropriate, to the Study Manager and the reviewing IRB at completion of the study. This report will be completed within 3 months of the study closure date.

9. Acceptance Criteria

Glucose

95% of all glucose results in the study should be within $\pm 15\%$ of the comparator results across the entire claimed measuring range of the device and 99% of all SMBG results within $\pm 20\%$ of the comparator results across the entire claimed measuring range of the device.

	Method Comparison/User Evaluation of the i-SENS Self-Monitoring Blood Glucose / β-Ketone System(CareSens PRO GK BT)	Document No. BGM-2205084
	Authorized approval of controlled documents is required for external release.  Controlled Document  Uncontrolled Document	Version No. 2

β -ketone

95% of the individual ketone results in this study should be within $\pm 0.3\text{mmol/L}$ at concentration $< 1.5\text{mmol/L}$ and within $\pm 20\%$ at concentration $\geq 1.5\text{mmol/L}$ of the comparator results.

10. Data Presentation and Data Analysis Method

For data analysis, a linear regression study will be performed using Passing-Bablok analysis with confidence bands for the regression line (95%). Passing-Bablok analysis is a robust analysis method for it takes account of extreme data points, and it does not assume a normally distributed measurement error, therefore is reliable when testing equality of biometrical evaluation. Accuracy will be determined based on:

$$\text{PD (Percent Difference)} = 100 * |T-R| / R \leq 15 \text{ \%}.$$

When T= device result and R= Laboratory reference method result.

Also a bias plot will be produced and the accuracy will be presented in an error interval tables.

Table 2. Summary of data within specified mg/dL of the comparator method for glucose concentrations across the entire range

Within $\pm 5\%$	Within $\pm 10\%$	Within $\pm 15\%$	Within $\pm 20\%$
X/Y (%)	X/Y (%)	X/Y (%)	X/Y (%)

Table 3. Summary of data within specified mmol/L of the comparator method for β -ketone concentrations across the entire range

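### The accuracy percentages are conditional on an evaluable reading, so no planned figure shows what share of the untrained people who tried obtained an acceptable result

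*Combined protocol and SAP*

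**What the plan says.** The first objective in Section 2 is about people: "To determine if untrained people with or without diabetes or pre-diabetes can obtain acceptable glucose and" β-ketone results from a fingerstick. The criteria listed under it, repeated in Section 9, are about results: "95% of all glucose results in the study should be within" ±15% of the comparator, "99% of all SMBG results within" ±20%, and for ketone "95% of the individual ketone results in this study should be within" ±0.3 mmol/L or ±20%, depending on concentration. Section 10 presents them as X/Y tables and does not define Y.

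Section 3 sets the size for glucose as "at least 350 evaluable and different subjects". The ketone paragraph also refers to a minimum of 350 evaluable subjects.

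For the glucose self-test, Section 5.4 step 3 states: "Three successful fingersticks/lances are allowed maximum (actual lances on the finger) to get a meter result". It gives no outcome for a subject who reaches the limit without a reading. For the ketone self-test, step 4 states no limit at all.

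Note 2 to Section 4.3 says "no eligible subject data will be excluded from the data analysis", but the sentence opens by limiting itself to evaluable data. Section 5.8.3 lists five reasons for non-evaluability, and absence of a meter result is not one of them.

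**The concern.** A person who uses all the allowed lances and gets no reading has not obtained an acceptable result, so that outcome bears directly on the first objective. If it enters no planned rate, the study can report a pass without showing how many of those who tried succeeded. At stake is what the study can conclude about lay use. The accuracy of the readings that were obtained is not in question. The information needed is already collected: lances, step completion, error codes and problems encountered all go on the CRF. No planned analysis turns them into a success rate.

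**Working it through.** **Can a subject without a reading enter the X/Y tables?**

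1. Section 5.4 steps 4 and 5 time the comparator draw from the first evaluable meter reading. With no reading, nothing triggers the draw, so there is no pair.
2. Step 9 compares only evaluable meter results with the YSI and Rx Imola values.
3. Section 3 counts evaluable subjects, so this person does not count toward 350.
4. Section 10 says that missing data are noted with reasons, and Section 8.6 requires a report on subject disposition. Neither yields a rate. The questionnaire in Section 5.8.1 measures perceived ease, not success.

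The subject therefore drops out of every planned percentage, although no sentence says so.

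**How much could it matter?**

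Inputs from the plan are 350 evaluable subjects and thresholds of 95% and 99%. The 350 is attributed to FDA guidance with no calculation, so there is no derivation to reproduce. The no-reading rate f is not in the documents; the values below are assumptions. For simplicity, nobody is lost for any other reason.

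Smallest passing counts:
- ±15%: 0.95 × 350 = 332.5, so 333 (333/350 = 95.1%)
- ±20%: 0.99 × 350 = 346.5, so 347 (347/350 = 99.1%)

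Subjects who must try to give 350 evaluable results: N = 350/(1 − f), rounded up. Person-level share = passing results / N.

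| Assumed f | N | Bare ±15% pass, 333/N | Bare ±20% pass, 347/N | All 350 within limits, 350/N |
|---|---|---|---|---|
| 0 | 350 | 95.1% | 99.1% | 100% |
| 1% | 354 | 94.1% | 98.0% | 98.9% |
| 2% | 358 | 93.0% | 96.9% | 97.8% |
| 5% | 369 | 90.2% | 94.0% | 94.9% |

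In each row the planned X/Y figures would stay at 95.1%, 99.1% and 100%.

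**How many no-reading subjects before the person-level share falls below the threshold?** This needs no assumed rate. With x passing results, it is the whole part of x/threshold, minus 350.
- ±20%, all 350 within limits: 350/0.99 = 353.5, so 3 can be absorbed (350/353 = 99.2%) and 4 cannot (350/354 = 98.9%).
- ±15%, all 350 within limits: 350/0.95 = 368.4, so 18.
- ±15%, 340 within limits (97.1%): 340/0.95 = 357.9, so 7.

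The ±20% figure is the sensitive one.

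**The case against.** The strongest reply is that the plan never claims to report a share of people. Section 2 places the accuracy criteria directly under the first objective, and a percentage of results is a proper accuracy measure. That stands: the criteria are sound for what they measure and need no change. But they do not by themselves answer the question about people.

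A reader might infer that the protocol directs staff to remove and replace subjects who get no reading. It does not. Section 5.8.3 does not list them, no replacement rule is written, and the only reason Section 3 gives for exceeding 350 is to fill the glucose ranges. That they drop out and that enrolment runs on past them follows from how the pairs and the 350 are defined.

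A reader might also infer that error-prone users are the ones lost. The documents do not show this. Users who err but get a reading stay in, unless they declare the test incorrect themselves; in that case Section 5.8.3 uses the repeat. Nothing indicates who would end with no reading.

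Nor would these subjects vanish from the record. Error codes, missing data, disposition and device deficiencies are all documented, and the deficiency definition in Section 7.1 includes usability. This is fair, but none of it is a planned proportion.

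Finally, the percentages in the table pair assumed rates with a bare pass and are not evidence of bias in this trial. That also stands.

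**Conclusion.** The point holds as a gap between the objective and the analysis. The planned percentages are conditional on an evaluable reading, the first objective is not, and no planned figure bridges the two. The plan is silent on how subjects without a reading are handled.

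The effect is zero if everyone gets a reading. Otherwise its size is unknown. Under the stated assumptions, a bare ±15% pass of 95.1% corresponds to 93.0% of those who tried at a 2% no-reading rate and 90.2% at 5%. Four such subjects are enough to bring the ±20% person-level share below 99% even when every reading obtained is within limits.

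The stronger reading, that the plan overstates device accuracy or misreports a success rate, is not supported: it reports accuracy of results and makes no person-level claim. This is an inexpensive improvement that should be made before the data are seen. It does not invalidate the acceptance rule.

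**What to change.** Leave the acceptance criteria in Section 9 on evaluable results, unchanged. In Section 10, for glucose and ketone separately:

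- Define Y, and state how subjects without a reading are classified and whether enrolment continues past them.
- Report the numbers who began the self-test, obtained a reading, were evaluable, and were within limits.
- Add (a) the share of subjects who began and obtained a reading. For glucose this means within the three allowed lances. For ketone the plan must first define a completed attempt, because Section 5.4 states no limit.
- Add (b) the share with a result inside the accuracy limits, counting no reading as not acceptable. Subjects who had a reading but were lost to hematocrit, staff timing or discordant laboratory replicates (Sections 5.6.2, 5.7.2 and 5.8.3) are shown separately and kept out of this denominator, so that staff or laboratory faults are not charged to the lay user.
- Give (a) and (b) exact 95% confidence intervals, as Section 5.8.1 already does for the questionnaire.

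Report (b) beside the acceptance result when concluding on the first objective, without a new pass threshold.

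The cost is a few more table lines, largely from fields already on the CRF, and a definition of a ketone attempt. The downside is a possibly less favourable figure next to the acceptance result.
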